To include participants from Cohort 2, we conducted a secondary, factorial analysis of the impact of the two interventions and their combination, using cohort as a factor, that was planned when we randomized participants whose clinics cared for ≤ 2 participants.

To determine the influence of the assigned intervention mediated via its impact on TUD medication use, and varenicline use specifically, the unmediated impact of the study interventions on abstinence, and the impact of TUD medication use and varenicline use specifically on abstinence we conducted mediation analyses using the combined cohorts. We assessed associations between intervention assignment, TUD medication use, and year-2 abstinence via path analyses based on logistic regression. Separate analyses assessed the impact of taking any TUD medication and varenicline specifically. Estimates of the indirect effect were computed per each imputation run and pooled using Rubin's method.

2. Statistical methods.

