Aim 1. Hypothesis 1a. *Those who receive AD+CHW will demonstrate higher rates of biochemically verified tobacco abstinence than those who receive usual care (TAU).* The primary outcome will be the proportion of smokers who are abstinent at their Year Three Assessment. This will be 12-24 months after randomization to study interventions because assessments are conducted in the pragmatic setting of the annual psychiatric rehabilitation team meetings. This smoking abstinence rate will be compared between the two groups using a generalized linear mixed models logistic regression, with random effect for clinic, assumed to be normally distributed [114]. **Hypothesis 1b.** *Those who receive AD+CHW will demonstrate higher rates of biochemically verified tobacco abstinence than those who receive AD only.* This rate will be compared between the two groups using logistic regression. **Hypothesis 1c.** *Those who receive AD will demonstrate higher rates of biochemically verified tobacco abstinence than those received TAU.* This rate will be compared between the two groups using generalized linear mixed models logistic regression. Hypothesis 1d. Participants assigned to receive CHW will demonstrate a higher rates of biochemically verified, 7-day point-prevalence tobacco abstinence than those assigned to TAU at the Year 3 Assessment. This will be tested with factorial analysis in the combined sample, using cohort as a factor. Additionally, we will compare MassHealth pharmacy claims data for smoking cessation medications (varenicline, bupropion and nicotine replacement therapy) to examine differences in prescribing patterns of providers randomized to AD compared to those randomized to TAU. We will also examine the effect of the interventions on rates of participants filling prescriptions for smoking cessation medication (i.e. AD, AD+CHW, CHW, TAU)

Aim 2: Hypothesis 2. *Those who receive AD+CHW will demonstrate improved Quality of Life compared to those who receive usual care, as assessed with the SF-1 (Overall Health).* We will assess this hypothesis with a random effects model with baseline, duration of follow up, and treatment group as covariates and a clinic random effect. We will use data from the last visit during the study as the dependent measure.

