Exploratory Aim 3: Through data collected by the RAs for both AD+CHW and TAU groups, we will identify differences in care processes that will be suggestive of specific mechanisms. The main components of the intervention are i) AD to prescribers, which is designed to increase the number of smoking cessation interventions initiated including prescriptions written and referrals for behavioral treatment; and ii) the availability of CHW

support to patients and providers, which is intended to improve client engagement with prescriber recommended tobacco treatment, including increasing access to, and use of tobacco treatment pharmacotherapies and attendance at behavioral smoking cessation treatment. The CHW, through encouraging cessation attempts and through client support, is expected to increase the effectiveness of the pharmacotherapies and behavioral groups, and reduce relapse risk. We will conduct exploratory analyses examining differences in self reported prescriptions received, prescriptions filled, and smoking cessation groups attended by study arm using linear mixed effects models with clinic random effects.

Exploratory Aim 4. Hypothesis 4a: *Participants with schizophrenia and schizoaffective diagnoses will demonstrate lower absolute rates of biochemically-verified, 7-day point-prevalence tobacco abstinence than those with other diagnoses.* This rate will be compared between the two groups using generalized linear mixed models logistic regression.

Hypothesis 4b. *Participants with schizophrenia and schizoaffective diagnoses will a demonstrate larger effect of treatment (AD+CHW) vs no treatment (TAU).* This effect will be compared between the two groups using generalized linear mixed models logistic regression. These hypotheses are underpowered to detect an effect and are considered to be exploratory only.

Aim 5: We will use an interactive convergent design, as the emerging qualitative and quantitative data findings will inform respectively additional analyses. Our interactive intramethod approach or “iterative approach” will allow for us to generate hypotheses resulting from the qualitative data analysis which we will examine quantitatively using Year 3 data to further inform the joint display analysis.

Quantitative Data Analysis

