The quit rate of 5% in the usual care group is also conservative, since the average cessation rate across 6 randomized clinical trials summarized in the Tsoi et al Cochrane Review of smoking cessation studies in adults with schizophrenia was 4% at 12 weeks among smokers with SMI who expressed intention to quit smoking within 30 days, set a quit date and received placebo and behavioral smoking cessation treatment. Those in the usual care group are unlikely to receive similarly intensive behavioral smoking cessation treatment [28], further supporting the conservative nature of the estimated 5% quit rate in the usual care group. We used this higher than expected cessation rate for the TAU group in the simulation in order to consider the possibility that publication of the results from our previous work [28, 37, 40] may change clinical practice without the concerted effort proposed under this project, though this has not been observed to date.[3] The variation of the parameter that determined the “clinic effect” was chosen so that the standard deviation of the probability of quitting among different clinics was 9% in the AD+CHW group and 3% in the usual care group. This differential variability reflects the floor effect of the small proportion of quitters in the usual care group, and the variability associated with the intervention in the AD+CHW group. The resulting overall intraclass correlation coefficient of 3% is typical for this type of study [115]. We then used this logistic model to simulate whether each patient would be abstinent at the Year Two assessment.

Our simulation resulted in over 95% power to detect a significant difference in the proportion of patients abstinent at the Year 3 assessment. As a sensitivity analyses, we increased the standard deviation of the parameters governing the variation in the quit rates by a factor of 50%. This would increase the overall intraclass correlation to 7% and reduce the power to 87%. If we considered only patients with schizophrenia spectrum disorders, which is a planned subgroup analysis, we would have 77% of the patients in this subgroup analysis. This would still give 94% power to detect an effect in those with a schizophrenia spectrum disorder.

Missing data

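### The mediation path analyses make no stated allowance for clinic, so intervals for contrasts of AD-containing arms with TAU would be too narrow if the plan is followed as written

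*Combined protocol and SAP*

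**What the plan says.** Section VII.1 (Analytic Plan) says that "we conducted mediation analyses using the combined cohorts", and gives the method as: "We assessed associations between intervention assignment, TUD medication use, and year-2 abstinence via path analyses based on logistic regression". On missing data it adds: "Estimates of the indirect effect were computed per each imputation run and pooled using Rubin's method". It does not say how the variance is obtained within an imputation, whether clinic enters the models, or on what scale direct and indirect effects are expressed.

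Section VII.2 (Statistical methods) words its other models differently:

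- Hypothesis 1a (AD+CHW v TAU): "generalized linear mixed models logistic regression, with random effect for clinic, assumed to be normally distributed".
- Hypotheses 1c, 4a and 4b: the same mixed-model family.
- Aim 2: a clinic random effect.
- Exploratory Aim 3, which covers prescriptions received and filled: "using linear mixed effects models with clinic random effects".
- Hypothesis 1b (AD+CHW v AD, a comparison within clinics): "This rate will be compared between the two groups using logistic regression".

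On the size of clustering, Section VII.4 (Sample Size Calculations) says: "The resulting overall intraclass correlation coefficient of 3% is typical for this type of study". It uses 7% as a sensitivity value.

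**The concern.** In Cohort 1, AD is allocated to whole clinics and delivered to their prescribers, so medication use, the mediator, can be expected to vary by clinic. Abstinence is assumed by the plan itself to do so. A logistic regression that treats patients as independent understates the variance of any contrast between clinic-randomised arms. Rubin's rules add between-imputation variance to the average within-imputation variance. They do not repair a within-imputation variance that ignores clinic.

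At stake is the analysis meant to show how far the interventions work through medication, and through varenicline in particular. If clinic is ignored, the AD effect on medication use and the part of its effect on abstinence that bypasses medication will both look more certain than they are.

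**Working it through.** **Inputs.** From Section VII.4: 40 clinics, 900 analysed patients, ICC 0.03 (sensitivity 0.07). From Section VII.1: one third of clinics to TAU, two thirds to AD, with half the patients at AD clinics offered a CHW. This gives about 13 TAU and 27 AD clinics and about 300 patients per arm. Assumed, because the plan is silent: two-sided 0.05, equal clinic sizes, and the abstinence ICC applied to medication use.

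**Design effect,** 1 + (m − 1) × ICC, where m is patients per clinic in the arm:

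- TAU: m = 900/40 = 22.5, giving 1.645 (ICC 0.03) and 2.505 (ICC 0.07).
- AD+CHW, or AD alone: m = 300/27 = 11.1, giving 1.303 and 1.707.
- All AD-clinic patients: m = 600/27 = 22.2, giving 1.637 and 2.486.

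**Check against the plan's own figure.** The first row of Table 1 gives power 0.96 for TAU 0.05 v AD+CHW 0.16 at ICC 0.03.

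- SE = √(0.05×0.95×1.645/300 + 0.16×0.84×1.303/300) = √0.000844 = 0.0291.
- z = 0.11/0.0291 = 3.79, and power = Φ(3.79 − 1.96) = 0.966.
- A simulation of the mixed model gave 0.956.

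The inputs therefore reproduce this figure.

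**Interval width if clinic is ignored** (equal prevalence in the two arms):

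- One AD-containing arm v TAU: √[(1.645 + 1.303)/2] = 1.21 at ICC 0.03, and √[(2.505 + 1.707)/2] = 1.45 at 0.07.
- All AD-clinic patients v TAU: √[(1.645/300 + 1.637/600)/(1/300 + 1/600)] = 1.28, and 1.58 with the 0.07 values.

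Correct intervals are thus 21–28% wider at ICC 0.03 and 45–58% wider at 0.07. A nominal 5% test has actual size 2[1 − Φ(1.96/ratio)]: about 11–13% and 18–22%. These sizes apply to the effects of arm on medication use and on abstinence, not to the indirect effect.

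**Sensitivity to clinic number.** Section VII.4 allows up to 60 clinics. With 20 TAU and 40 AD clinics, m is 15 for TAU, 7.5 for one AD-containing arm and 15 for all AD-clinic patients.

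- ICC 0.03: √[(1.42 + 1.195)/2] = 1.14 and √1.42 = 1.19.
- ICC 0.07: √[(1.98 + 1.455)/2] = 1.31 and √1.98 = 1.41.

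The problem shrinks but remains.

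**Mediation quantities.** A 2,000-run simulation of the clinic-randomised contrast assumed medication use of 20% rising to 35% and an odds ratio of 3 for medication on abstinence. Coverage of nominal 95% intervals:

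| Quantity | ICC | Ignoring clinic | Clinic-robust |
|---|---|---|---|
| Direct effect | 0.03 | 0.903 | 0.949 |
| Direct effect | 0.07 | 0.840 | 0.933 |
| Indirect effect (product) | 0.03 | 0.900 | 0.924 |
| Indirect effect (product) | 0.07 | 0.858 | 0.932 |

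When the intervention has no effect on medication use, the unadjusted interval for the indirect effect covers 0.960 at ICC 0.03 and 0.928 at 0.07. For the CHW contrast within clinics, the ratio of true to unadjusted SE is 0.95–1.04, so no correction is needed.

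**Scale.** Take abstinence 5% v 16%, medication use 20% v 35%, and an odds ratio of 2 for medication on abstinence (the last two assumed).

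- Arm to medication: logit 0.35 − logit 0.20 = 0.767. Medication to abstinence: ln 2 = 0.693. Product: 0.532.
- The direct coefficient is 1.183, so direct plus product is 1.715, against a total log odds ratio of 1.286.
- The share mediated would read 0.532/1.715 = 31%, against 0.113/1.286 = 9% for the natural indirect effect on the log-odds scale and 13% on the risk scale.

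**The case against.** The plan never says that clinic is ignored. A mixed logistic model is also based on logistic regression, and the mediation text is a short summary. This stands as a caution: the omission is inferred. The inference is nonetheless strong, because the plan specifies mixed models or clinic effects for its other between-clinic comparisons and uses the bare wording only for the within-clinic Hypothesis 1b.

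The exposure is only partly clinic-randomised. CHW is allocated by participant, both within AD clinics and in Cohort 2, and intervals for that contrast are about right. This stands and limits the point to AD-containing arms against TAU.

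A reader might infer that a finding of mediation through medication or varenicline could be an artefact of clustering. The check does not support that at the plan's ICC: with no effect on medication use, the unadjusted interval for the indirect effect covers 0.960. Under a real effect, about half the shortfall at ICC 0.03 remains after clinic-robust correction (0.924 against 0.900), so not all of it comes from ignoring clinic.

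A reader might also infer that direct and indirect effects are reported on odds scales that cannot be compared. The plan states no scale and no estimator. The failure to add up arises if logit coefficients are multiplied. Taking the total minus the direct coefficient stays close to the natural indirect log odds ratio (0.07–0.42 against 0.08–0.44 over the scenarios examined).

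Finally, the mixed models for Hypotheses 1a and 1c and for prescriptions give a cross-check on the overall effect and on the path to medication. They give no valid interval for the direct or indirect effect.

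**Conclusion.** The point holds for the clinic-randomised AD component. As written, the mediation models omit a feature of the design that the plan respects elsewhere. For AD-containing arms against TAU, intervals for the path to medication use and for the direct and total effects on abstinence need to be about 21–28% wider at ICC 3% and 45–58% wider at 7%. For the indirect effect, coverage is about 0.90 and 0.86 under a real effect, and close to nominal at 3% when the path to medication is null.

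These figures rest on 40 equal-sized clinics, a medication-use ICC equal to that for abstinence, and two-sided 0.05. The mediation coverages also rest on the assumed medication-use rates and odds ratio. They describe Cohort 1. The combined-cohort analysis was not recalculated, but Cohort 2 (155 participants at 111 clinics, about 1.4 each) is hardly clustered and contains no AD arm, so a combined figure might be slightly lower.

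This is a secondary analysis. It should be corrected, but the primary test of Hypothesis 1a does not depend on it. The absence of a stated effect scale is a lesser matter that needs clarification.

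**What to change.** Fit both path regressions (intervention to medication use; intervention and medication use to abstinence) with the clinic random effect already specified for Hypothesis 1a, or resample whole clinics within each imputed data set to obtain the variance. Then pool by Rubin's rules.

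As a secondary clarification, state one common scale and report total, direct and indirect effects on it. Differences in abstinence probability, obtained by standardisation, would serve.

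No new data are needed. The cost is a few lines of text, more computation (most with a clinic bootstrap inside each imputation) and wider intervals. Because the mediation paragraph is written in the past tense, the practical step may be a re-run, or a statement that clinic was in fact accounted for and how.

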As noted above, after enrollment was complete, but before the randomization, the protocol was amended because 13% (155 of 1165) of enrolled participants received primary care at 111 clinics that each served ≤ 2 enrolled participants. Because it was beyond the scope of the project to provide AD to so many clinics, prior to randomization, the decision was made and approved by the sponsor to include these 155 enrolled participants in a second cohort in a stratified randomization, such that Cohort 1 (AD-eligible) comprised participants seen in primary care clinics serving ≥ 3 enrolled participants described above. Cohort 2 (AD-ineligible) comprised participants whose primary care clinic served ≤ 2 enrolled participants who were randomized to CHW or TAU in a 1:1 ratio.

The patient population will consist of approximately 1300 adult outpatient smokers with SMI who receive psychiatric rehabilitation services through CBFS and ACT programs at Bay Cove Human Services and Vinfen Corporation. This includes adults primarily with schizophrenia spectrum disorders and bipolar disorder.

Inclusion/exclusion criteria:

Primary care clinics/physicians/nurses/care team: There are no requirements for clinics to be included or excluded except that they provide medical care to people with SMI who smoke and who are served by the CBFS and ACT psychiatric rehabilitation systems of Bay Cove and Vinfen. There are no exclusion criteria for prescribers related to specialty (e.g. internal medicine, psychiatry, pulmonary medicine, family medicine, clinical nurse specialist), experience with smoking cessation therapies, or experience working with people with SMI.

Since the patient and their prescriber will decide together on the timing of initiation of any pharmacotherapeutic cessation aid, there will be no exclusion criteria for patients due to medical illness or psychiatric symptom severity or stability or substance use.

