their primary care team in the past year. Study staff will attend the IAP meeting for those who agree. Study staff will follow a brief script to explain the study to participants, to inform them that participation in the 3 brief annual surveys is entirely voluntary, that their decision of whether or not to participate will in no way impact their ongoing psychiatric rehabilitation services or primary care, and to obtain verbal consent from those who agree to answer the smoking and smoking-treatment-related questions. Participants will be asked to complete the survey on 3 occasions, on an annual basis, once before clinic randomization (Year One, baseline) and twice after the intervention has been implemented (Years 2 and 3). We expect 85-90% of potential participants (n=900) to agree to participate in this 5-minute survey once a year for 3 years at their annual IAP meeting or other setting in which they interact with their psychiatric rehabilitation team members. Those who complete the survey will be reimbursed \$5 for their time. Study staff who administer the survey will be trained in the process for obtaining verbal consent, in privacy standards such as the HIPAA privacy rule, and in adherence to the study protocol, including data collection methods.

Procedures protecting confidentiality.

Staff employed at the human service agencies providing psychiatric rehabilitation services (Bay Cove Human Services and Vinfen) will create a database that assigns a study identification number (random numeric value) to each of their clients that they have identified as a smoker. The names of eligible participants under their care and the key linking these names to study IDs will be available only to the psychiatric rehabilitation agency staff. MGH staff who administer the surveys in Years 1-3 will have access only to study IDs and, at the time of the survey, to first names of participants. MGH study staff will identify surveys with study IDs only.

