Indication of whether prescriptions were refilled
Limited set of patient study data
Study arm
Age group (ten year increments)
Gender
Self-reported smoking cessation medication use (varenicline, bupropion, NRT) at baseline, Y1, Y2
Race
Ethnicity
Self reported abstinence at Year 1 (baseline), Year 2 (intervention year 1), and Year 3 (intervention year 2)
The use of pharmacy data involves no more than minimal risk to participants. All PHI disclosed to MassHealth will be protected using secure transfer and storage and we will disclose the minimum amount of data necessary (e.g., IDs, intervention date windows, age groups) that pose minimal risk to participants. No PHI will be included in any of the data files received from MassHealth or analyzed by MGH staff and the de-identified data will be protected. Only aggregate results will be presented.

These data will be stored on Partners servers and behind the Partners Information Security firewall. Data will not leave the performance site and will not be stored on removable devices such as laptops or external drives. Access control to the data is maintained centrally via Active Directory, and will not be accessible to persons outside of the study team (access is by username and password authentication).

Request for Waiver of Written Consent

1) The proposed research involves no more than minimal risk to participants.

We propose to study the effects of enhancements to a system of usual care delivery on primary care provision of evidence-based ‘standard of care’ treatment for tobacco

addiction and smoking cessation rates. Patient safety will be overseen by primary care providers and the psychiatric rehabilitation team in the course of usual care.

Participants will be asked to respond to a brief 5-minute survey once a year for 3 years and may be offered CHW support as a supplement to their usual psychiatric rehabilitation supports, which they can either accept or decline, as they do for other psychiatric rehabilitation services, such as housing support and vocational support. Whether a person agrees to participate or not, their primary care clinic staff may receive academic detailing regarding safety and efficacy of standard of care smoking cessation treatment for people with psychiatric illness.

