Only aggregate results across groups of providers or patients will be analyzed and shared; no information on individual providers or patients will be generated or shared. We will not publish or report any cell size with 10 or fewer participants in accordance with data suppression policies.

V. STUDY PROCEDURES

This study aims to compare the effects of service interventions, AD+CHW, AD, CHW and TAU, on smoking outcomes in a large community psychiatric rehabilitation system of care.

Allocation concealment: Intervention allocation will be randomly assigned by computer generated list.

Blinding: Neither participants nor providers will be blind to the intervention assigned. Research coordinators who conduct the surveys with all participants will be blind to intervention assignment to the extent possible as the participant may volunteer information that makes study assignment clear to the coordinator.

1. Overview of Survey Visits:

Research assistants will attend the annual, scheduled CBFS and ACT rehabilitation team treatment planning meeting in the community to conduct an annual survey when the psychiatric rehabilitation team is engaging with the patient. The schedule of psychiatric rehabilitation team meeting is fixed according to the month of enrollment in CBFS or ACT, and the study assessments will accommodate this schedule. The brief annual survey will take 5 minutes for most participants. Those who complete the baseline survey will be asked to repeat the survey at their next two annual psychiatric rehabilitation team meetings.

2. Survey Items

2.1 **Demographics:** age, sex, race, living situation (Group Home/Supervised Housing or Independent Living) (Baseline Assessment only)

2.2 **Smoking Status:** If smoking: number of cigarettes smoked per day; if prior smoker: time since last cigarette and quitting method.

2.3 **Smoking cessation services in the past year:** If smoking: report of whether smoking status was assessed by their primary care physician or nurse, whether advice to quit smoking was given, whether prescription of pharmacotherapeutic cessation aids and/or referral to behavioral smoking cessation treatment were offered or made.

- If pharmacotherapeutic cessation aids were prescribed, we will ask if the was filled, and, if so, whether the medication was used, and, if so, for how long.

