4.5 Mixed Methods Research Questions

MRQ 1a. Among patient participant, CHW and primary care provider (PCP) stakeholders, what are the barriers and facilitators to use of the intervention and how do these compare according to performance level, namely, patient quitters, PCP prescribers, and CHW facilitators?

MRQ 1b. Among patient participant, PCP, and CHW stakeholders, what are the barriers and facilitators to use of the intervention and how do these compare according to level of engagement?

MRQ 2a. How do the PCPs, grouped by primary care clinic, differ by performance level and how do their experiences with the intervention, and the barriers and facilitators compare across these groups?

MRQ 2b. What is the association between engagement with the AD intervention among high or low performers, and how did barriers and facilitators experience compare across these groups?

QQ (Qualitative Question) 3. What barriers and facilitators do stakeholders, such as clinical, payor and policy leaders anticipate impacting the implementation of the integrated smoking cessation treatment?

Time and Events Table

VII. BIOSTATISTICAL ANALYSIS

1. Analytic Plan.

With the original 3-arm design, 1/3 of clinics that serve 3 or more smokers with SMI will be randomly assigned to the TAU arm and 2/3 will be assigned to receive AD. At the clinics assigned to AD, half of the smokers with CBFS or ACT services who participated in the baseline assessment will be randomly assigned to be offered CHW support to quit smoking. The primary outcome measure will be the difference in smoking rates and self-reported overall health from year 1 to year 3 between those assigned to AD+CHW compared to TAU. In secondary analyses, we will also compare these outcomes in the AD+CHW group compared to the AD group, and in

Year	1	R	2	3
Study Visit	1	A	2	3
Questions		N		
Demographics (age, sex, race, living situation)	X	D		
Smoking Status	X	O	X	X
Heaviness of Smoking Index (HSI)	X	M	X	X
Smoking questionnaire	X	I	X	X
Single item Health related quality of life (SF-1)	X	Z	X	X
		A		
		T		
Biomeasure		I	X	X
Exhaled CO (in those who report being non-smokers)	X	O		
Quantitative Data Collection				X
Payment	\$5	N	\$5	\$5

AD compared to TAU. For participants who receive primary care from a clinic that serves two or fewer adult smokers with SMI, we will randomize half to receive CHW services. This comparison can be kept entirely separate from the main analysis of AD vs AD+CHW vs TAU

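### Current smoking is not re-confirmed at the Year 1 survey, so a participant already abstinent before randomisation can count as a Year 3 success and dilute the primary AD+CHW versus TAU effect

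*Combined protocol and SAP*

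**What the plan says.** **Who enters.** Section III describes the population: "The patient population will consist of approximately 1300 adult outpatient smokers with SMI". Section IV has agency staff give a study ID "to each of their clients that they have identified as a smoker". Sections IV, V.3 and VII (Missing data) also speak of clients who smoke now. The word is not tied to a look-back period, an amount smoked, or the answer given at the Year 1 survey.

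**Who is randomised.** Under section IV, randomisation follows agreement to the baseline survey. The only stated ground for taking a study ID off the list is refusing the survey and any further approach.

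**What is recorded at Year 1.** The Time and Events Table has a row "Exhaled CO (in those who report being non-smokers", marked at Year 1. Survey item 2.2 has a branch, "if prior smoker: time since last cigarette and quitting method". The claims-linked file carries "Self reported abstinence at Year 1 (baseline), Year 2 (intervention year 1), and Year 3 (intervention year 2".

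**What is analysed.** For Hypothesis 1a, section VII.2 states: "The primary outcome will be the proportion of smokers who are abstinent at their Year Three Assessment". It compares arms by "generalized linear mixed models logistic regression, with random effect for clinic, assumed to be normally distributed". It names no baseline covariate, although Aim 2 in the same section does. Section VII.1 words the primary outcome differently, as a year 1 to year 3 difference in smoking rates, and gives no model for that version. Under Missing data, Year 1 data serve only to help impute missing Year 3 outcomes.

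**The concern.** The trial asks whether AD+CHW gets smokers to quit. Section VII.4 builds its AD+CHW rate from smokers: 65% try, 30% of those succeed and roughly 20% relapse, so 0.65 × 0.30 × 0.80 = 0.156, taken as 15%. A participant who had stopped before randomisation and is still abstinent at Year 3 adds a success that does not belong to that calculation.

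If such people are equally common in both arms and stay abstinent equally often, they raise both rates by the same amount. The risk difference shrinks a little, and the risk and odds ratios shrink more. Variance rises because both proportions move up from the floor.

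The denominator is also open. One analyst could read the smokers in the outcome definition as everyone on the agency list, another as those smoking at Year 1. Under the section VII.1 wording, a third could compute change from Year 1. These give different primary results.

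**Working it through.** **Inputs from the documents**
- Analysed sample 900 and 40 clinics (VII.4). One third of clinics go to TAU and two thirds to AD, with half of AD-clinic participants offered a CHW (VII.1). That is about 300 per arm, with about 13 TAU clinics and 27 AD clinics.
- Abstinence 15% versus 5% and ICC 0.03 (VII.4).

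**Assumptions**
- Two-sided 0.05. The plan states no level for this test.
- *f*, the share abstinent at Year 1, is not in the documents; 2% and 5% are shown.
- *m*, the share of those people abstinent at Year 3, is 0.40 to 0.80, equal in both arms. The low end extends the plan's 20% relapse per six months over two years: 0.8⁴ = 0.41.

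**Formulas**
- Design effect = 1 + (cluster size − 1) × ICC; effective n = n / design effect.
- Arm rate = (1 − f) × quit rate + f × m.
- SE = √[p₁(1 − p₁)/n₁ + p₂(1 − p₂)/n₂]; power = Φ(difference/SE − 1.96).

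**The plan's own figures first.** With 450 versus 450 in 20 clinics each, cluster size is 22.5, the design effect 1.645 and effective n 273.6. SE = √(0.175/273.6) = 0.0253 and power = Φ(1.99) = 0.977, in line with the stated power of over 95%. At ICC 0.07 the same method gives 0.893 against the stated 87%. In the three-arm layout at 16% versus 5% it gives 0.966; the first row of Table 1 states 0.96.

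**Three-arm layout at 15% versus 5%**
- TAU: 300/13 = 23.1 per clinic, design effect 1.662, effective n 180.5.
- AD+CHW: 300/27 = 11.1 per clinic, design effect 1.303, effective n 230.2.
- No baseline abstainers: SE = √(0.0475/180.5 + 0.1275/230.2) = 0.0286; power = Φ(1.54) = 0.938.

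**One diluted case in full (f = 5%, m = 0.80)**
- TAU: 0.95 × 0.05 + 0.05 × 0.80 = 0.0875.
- AD+CHW: 0.95 × 0.15 + 0.05 × 0.80 = 0.1825.
- Difference 0.095; risk ratio 0.1825/0.0875 = 2.09.
- SE = √(0.0798/180.5 + 0.1492/230.2) = 0.0330; power = Φ(0.92) = 0.820.

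| f | m | TAU | AD+CHW | Risk ratio | Power, all kept | Power, Year 1 smokers only |
|---|---|---|---|---|---|---|
| 0 | – | 0.0500 | 0.1500 | 3.00 | 0.938 | 0.938 |
| 2% | 0.40 | 0.0570 | 0.1550 | 2.72 | 0.914 | 0.935 |
| 2% | 0.80 | 0.0650 | 0.1630 | 2.51 | 0.895 | 0.935 |
| 5% | 0.40 | 0.0675 | 0.1625 | 2.41 | 0.873 | 0.930 |
| 5% | 0.80 | 0.0875 | 0.1825 | 2.09 | 0.820 | 0.930 |

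The last column keeps 5% and 15% and cuts each arm to 300 × (1 − f), with cluster sizes reduced to match. At f = 5% that is 285 per arm, effective n 175.1 and 221.5, SE 0.0291 and power Φ(1.48) = 0.930.

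Using a pooled variance under the null lowers the starting power to 0.919 and the other figures by roughly two points, with the same pattern.

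**The case against.** The strongest reply is that the plan does target people who smoke. Agencies track smoking as part of usual care, several sections use the present tense, and the outcome itself refers to smokers. A reader might infer that the trial has no smoking requirement at all. The documents do not support that: what is missing is re-confirmation at the survey and a rule for those who have already stopped. On a list of tracked smokers they may be few.

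Some of the signs that the plan expects baseline non-smokers are weak. One survey serves all three years, so the prior-smoker branch is needed later anyway, and the claims file simply lists every time point. The Year 1 CO mark is the real evidence. The table's layout is damaged in the text copy, but Year 1 is the natural reading. It shows that the case was provided for, not how often it occurs.

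A reader might also infer that neither arm could influence such a person's Year 3 result. Exploratory Aim 3 in section VII.2 says otherwise: the CHW is expected to lower relapse risk. If so, *m* differs by arm and the dilution is smaller than shown.

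Nor does the gap bias the comparison. An analysis of everyone randomised is valid and suits a pragmatic trial, and chance imbalance between clinics is already covered by the test's error rate. What stands is loss of power, a smaller effect estimate and an undefined denominator.

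**Conclusion.** The point holds as a moderate weakness. Anyone already abstinent at Year 1 would be randomised and could count as a Year 3 success, with nothing in the primary model to account for it. On the stated assumptions, a 2% share costs about 2 to 4 points of power and a 5% share about 6 to 12 points, while restriction to Year 1 smokers costs about 1 point or less. At 5% the risk ratio drops from 3.0 to between 2.1 and 2.4.

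The size depends on a share the documents do not report and on equal persistence of abstinence in the two arms. The conflict between the outcome wordings in sections VII.1 and VII.2 does not depend on either.

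**What to change.** In section VII.2:
- Define the H1a analysis set as randomised participants who were smoking at the Year 1 survey. Apply the verification in survey item 2.6 to Year 1 reports of abstinence, and treat a report that is not verified as smoking.
- Report the number excluded in each arm.
- Give the all-randomised result, adjusted for Year 1 smoking status, as a sensitivity analysis.
- Reconcile the outcome wording of sections VII.1 and VII.2.
- State when the rule was set. Section VII.1 describes some analyses as already conducted, so readers need to know whether it preceded sight of the outcome data.

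The cost is a small loss of participants (6 per arm of 300 at 2%, 15 at 5%) and a primary set that is no longer everyone randomised. No new data are needed. Because Year 1 status is recorded before randomisation, restricting on it leaves the randomised comparison intact.
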